6.2.3. Pharmacokinetics and Exploratory

Flow cytometry for diagnosis will be performed at screening on both bone marrow (when available) and peripheral blood samples (all patients). Flow cytometry will be performed on blood samples at other visits at the investigator's discretion.

Pharmacokinetics of MS-553 and/or its metabolites will be studied. Please see table below for timing of PK assessment. The exact time of each PK draw must be accurately recorded in the source document and on respective eCRFs.

	C1D1	C1D8	C2D1	C2D8	C3D8	C4D1	C4D8	C5D1
Cohort A1	Х	Х						
Cohort A2		Х		X1	X1	Х		
Cohort A2 DS1			Х					
Cohort A2 DS2			Х					
Cohort A3			Y					
Cohort B1								
≤200 mg BID		Х	Y					
>200 mg BID		Х		X1	X1	Y		
Cohort B2 & B3							1	
≤200 mg BID			Y					
>200 mg BID						Y		
Cohort C								
C1					Z	Х		Х
C2								Y

Table 7:Schedule of PK Assessments

DS1: Dose Schedule 1

DS2: Dose Schedule 2

X: PK sampling timepoints: MS-553 pre-dose, and 1 hr, 2 hr, 3 hr, and 4 hr (± 5 minutes) post-dose, and 6 hr (± 10 minutes) post-dose

Y: PK Sampling timepoint: MS-553 pre-dose

Z: PK sampling time points: 1 hr, 2 hr, 3 hr, and 4 hr (± 5 minutes), and 6 hr (± 10 minutes) post-venetoclax dose

1: Patients need to return for PK blood draws.

6.3. Correlative Science

[figure not shown]
Correlative studies are critical to understanding toxicity and efficacy of novel targeted agents. Tightly coupling correlative studies with clinical trials can help understand best next lines of therapies for patients as well as predictors of response and mechanisms of resistance in a much more rapid manner. The samples collected and procedures performed for correlative laboratory science are an integral part of this study. Complete details of correlative science sample collection, analyses and end points are provided in the Lab Manual.

6.3.1. Responsibilities

MingSight will coordinate the collection and analysis of all correlative science and exploratory studies.

[figure not shown]
6.3.2. Correlative Sciences Sample Collection Overview

There are three types of samples being collected for the correlative sciences studies to be performed. They are:

[figure not shown]

3) Pharmacodynamic samples (PKC-β Biomarkers) for the measurement of PKC-β signalling in cells isolated from whole blood.

will

6.3.3. Correlative Science Studies Description

[figure not shown]
Several key study time points for correlative sample collection are planned (see Section 6.3.2). For responding patients, some samples may be collected during follow up therapy.

[figure not shown]
will be ideally collected at Cycle 1 Day 1 using the

For Cohorts A1, A2, and B1

be collected immediately prior to dosing on Cycle 1 Day 1 and Cycle 1 Day 8 pre-dose and at 3 hr post-dose. For Cohort C1, PKC- β biomarker samples will be collected prior to dosing on Cycle 4 Day 1 and pre-dose and at 3 hr post-dose on Cycle 4 Day 8.

For all cohorts, research samples will be taken for cube and for CLL patients and Richter's from CLL. For all patients in Cohort A, additional research samples will be taken for

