- I agree to maintain all information supplied by MingSight Pharmaceuticals Inc. in confidence and, when this information is submitted to an Institutional Review Board (IRB), Independent Ethics Committee (IEC) or another group, it will be submitted with a designation that the material is confidential.

Printed Name of Investigator

Signature of Investigator

Date

SYNOPSIS

Name of Sponsor/Company: MingSight Pharmaceuticals, Inc.

Name of Investigational Product: MS-553

IND Number: 135339

Title of Study: A Phase I/II Dose-Escalation and Expansion Study of the Selective PKC-β Inhibitor MS-553 in Patients with Chronic Lymphocytic Leukemia/Small Lymphocytic Lymphoma

Phase: I/II

Comparator: None

Number of Subjects: Approximately 153

Study Sites: Up to approximately 15 sites

Study Design:

Single agent MS-553 cohorts (A-series):

This is a Phase I/II multi-center, open-label study of MS-553 in patients with chronic lymphocytic leukemia (CLL)/small lymphocytic leukemia (SLL). The first part of the study, the dose escalation portion **(Cohort A1**), will determine the safety of MS-553 and the maximum tolerated dose (MTD) or initial recommended Phase 2 dose (RP2D) of MS-553 monotherapy. After the MTD or initial RP2D is identified, an expansion cohort (**"Expansion Cohort A2**") of approximately 25 patients with refractory or relapsed CLL/SLL who (a) have failed at least two prior lines of therapies, or (b) have either acquired clinical and/or molecular resistance to a BTK inhibitor (i.e., BTK and/or PLCG2 mutation) after achieving initial response to a BTK inhibitor will be enrolled.

In addition, an **optional expansion cohort** ("**Expansion Cohort A3**") of approximately 25 patients with aggressive lymphoma, including Richter's transformation, diffuse large B-cell lymphoma (DLBCL) and mantle cell lymphoma (MCL) may be enrolled. At least 15 patients in this cohort shall be MCL patients.

additional patients will be enrolled in Cohort A2 to allow testing of two dose levels before a final RP2D can be declared.

The two dose schedules, designated as dose schedule 1 (DS1) and dose schedule 2 (DS2), are as follows:

Dose Schedule 1 (DS1)				
MS-553 Oral Daily Dose				
Week 1 150 mg BID				
Week 2 200 mg BID				
Week 3 and beyond 250 mg BID				
Dose Schedule 2 (DS2)				

	MS-553 Oral Daily Dose
Cycle 1 and beyond	225 mg BID

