3.1.1. Cohort A: MS-553 Monotherapy

The first part of the study, the dose escalation portion (Cohort A1), will determine the safety of MS-553 and the MTD or initial RP2D. After the initial RP2D is identified, an expansion cohort (Cohort A2) will be started at the MTD or initial RP2D, enrolling approximately 25 patients with relapsed/refractory CLL/SLL who (a) have failed at least two prior lines of therapies, or (b) have either acquired clinical and/or molecular resistance to a BTK inhibitor (i.e., BTK and/or PLCG2 mutation) after achieving initial response to a BTK inhibitor. In addition, an optional expansion cohort (Cohort A3) of approximately 25 patients with aggressive lymphoma, including Richter's transformation, DLBCL and MCL will be enrolled. At least 15 patients in Cohort A3 shall be MCL patients.

additional patients will be enrolled in Cohort A2 to further testing two dose levels before a final RP2D can be declared.

The two dose schedules designated as dose schedule 1 (DS1) and dose schedule 2 (DS2) are as follows:

	MS-553 Oral Daily Dose
Week 1	150 mg BID
Week 2	200 mg BID
Week 3 and beyond	250 mg BID

Dose Schedule 1 (DS1)

Dose Schedule 2 (DS2)

	MS-553 Oral Daily Dose
Cycle 1 and beyond	225 mg BID

Twenty of the 40 additional patients will be treated with DS1 and the other 20 patients with DS2. The patients will be allocated to either DS1 or DS2 in alternating fashion, according to the sequence of their enrollment. For example, the first enrolled patient will be allocated to DS1, the second patient to DS2, the third patient to DS1, the fourth to DS2, and so on.

The optional expansion cohort (Cohort A3) will be closed to accommodate the new dose testing plan.

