During the dose escalation period, intra-patient dose escalation will be permitted at the discretion of the study investigators and after discussion with the medical monitor and Sponsor, if the following criteria are met:

- The next higher dose for the regimen has been demonstrated to be safe by at least 3 patients and all 3 patients complete one cycle without experiencing any DLT.
- 2. The patient who will receive the higher dose has not experienced a DLT and has also completed at least 2 cycles of therapy at their current dose.
- 3. Intra-patient dose escalation can be increased only by one dose level at a time.

After completion of each dose escalation cohort, the SRC will review clinical safety and tolerability data as well as PK data available at the time for all patients in order to confirm dose escalation to the next dose level. Based on the SRC's review, a cohort may be expanded, or an intermediate or a lower-than-planned dose level or an alternative dosing schedule may be evaluated.

All patients will continue to be monitored for approximately 30 days (+7 days) after treatment discontinuation for development of any late treatment emergent adverse events. Any such late adverse events will be considered in the determination of the MTD/initial RP2D and dose schedule to be taken forward into the expansion phase of the study.

While the

MTD was not reached, an initial RP2D was identified. **Second Second** the SRC reviewed all available efficacy, safety, PK and PD data of Cohort A1 and some Cohort A2 patients and agreed on an updated RP2D with a ramp-up dosage regimen as shown in Table 3 below.

MS-553	Oral Daily Dose
Weeks 1 to 4 (Cycle 1)	150 mg BID
Weeks 5-8 (Cycle 2)	200 mg BID
Weeks 9 and beyond	250 mg BID
(Cycle 3+)	

Table 3:Initial Recommended Phase 2 Dose

The two new dose schedules are designated as dose schedule 1 (DS1) and dose schedule 2 (DS2) are as follows:

Dose Schedule 1 (DS1)

	MS-553 Oral Daily Dose
Week 1	150 mg BID
Week 2	200 mg BID
Week 3 and beyond	250 mg BID

Dose Schedule 2 (DS2)

	MS-553 Oral Daily Dose
Cycle 1 and beyond	225 mg BID

Twenty of the 40 additional patients will be treated with DS1 and the other 20 patients with DS2. The patients will be allocated to either DS1 or DS2 in alternating fashion, according to the sequence of their enrollment. For example, the first enrolled patient will be allocated to DS1, the second patient to DS2, the third patient to DS1, the fourth to DS2, and so on.

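### On the times visible in Section 6.3.3, Cohort A2's PKC-β pair falls on C1D8, with DS1 still in ramp-up and DS2 already on 225 mg BID, so it cannot compare the two schedules

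*Combined protocol and SAP*

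**What the plan says.** Section 6.3.3 gives one sampling rule, introduced by "For Cohorts A1, A2, and B1": samples are to "be collected immediately prior to dosing on Cycle 1 Day 1 and Cycle 1 Day 8 pre-dose and at 3 hr post-dose". The words naming the sample are blanked. The next sentence gives the matching rule for Cohort C1 and names PKC-β biomarker samples, so PKC-β is the natural reading. The visible text makes no separate provision for DS1 or DS2.

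Section 3.1.1 adds 40 patients to Cohort A2, 20 per schedule: "The patients will be allocated to either DS1 or DS2 in alternating fashion". The Synopsis gives DS1 as "Week 1 150 mg BID", then "Week 2 200 mg BID", then "Week 3 and beyond 250 mg BID". DS2 is 225 mg BID from the start. The stated purpose is to test both before a final RP2D is declared.

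Table 7 (Section 6.2.3) gives DS1 and DS2 their own PK rows, each with a full profile at C2D1 ("X: PK sampling timepoints: MS-553 pre-dose, and 1 hr, 2 hr, 3 hr, and 4 hr", with a further draw at 6 h). On the role of PD, Section 3.3.2 records that for the updated RP2D "the SRC reviewed all available efficacy, safety, PK and PD data of Cohort A1 and some Cohort A2 patients".

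**The concern.** The two schedules differ in two ways: DS1 ramps up over two weeks, and it ends at a higher dose (250 against 225 mg BID). A biomarker comparison that is meant to help choose between them should be taken when both are on the dose patients will stay on. C1D8 falls inside the DS1 ramp-up. A difference in PKC-β inhibition on that day would mix the schedule with the titration step, and the exposure order would be the opposite of the order at maintenance. That is a bias, so more patients would not remove it.

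There is also a pairing problem. In the DS1 and DS2 rows of Table 7 the PK profile is on C2D1, while the visible PD pair is on C1D8. In DS1 these are different doses, so exposure and inhibition could not be linked at 250 mg BID. A sample not taken at the right time cannot be recovered afterwards.

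**Working it through.** The plan states no size, power or criterion for a PD comparison (Section 8.4 says there is no formal hypothesis), so there is no figure to reproduce. The check is of dose and exposure by sampling day.

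**Inputs.** Doses: Synopsis and Section 3.1.1. Sampling times: Section 6.3.3 and Table 7. Half-life 10-14 h, Tmax 2-4 h and mostly dose-proportional exposure: Section 1.2.4 (healthy volunteers, single dose). **Assumptions:** a linear one-compartment oral model with dosing every 12 h and absorption rate ka of 0.6-1.5 per hour, which gives a Tmax of about 2.2-4.5 h.

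**Step 1: nominal dose behind each sample.**

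| Sample | DS1 (mg BID) | DS2 (mg BID) | Ratio |
|---|---|---|---|
| C1D8 pre-dose | 150 | 225 | 0.67 |
| C1D8, 3 h | first 200 mg dose, after a week of 150 | 225 | 0.89 |
| C2D1 pre-dose and 3 h | 250 | 225 | 1.11 |

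**Step 2: steady state.** Seven days is 168 h, or 168/14 = 12 to 168/10 = 16.8 half-lives. By C1D8 pre-dose both schedules are at steady state on their week 1 dose, so the exposure ratio equals the dose ratio, 150/225 = 0.67.

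**Step 3: C1D8 at 3 h.** Let S be the steady-state concentration per mg 3 h after a dose, and D the part of S that comes from the latest dose alone. DS1 has 150 × S plus an extra 50 × D; DS2 has 225 × S. So

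ratio = (150S + 50D) / 225S = 0.667 + 0.222 × (D/S).

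For a half-life of 12 h and ka = 1.0 per hour, k = ln 2/12 = 0.0578. On a common scale:
- D = exp(−3k) − exp(−3ka) = 0.841 − 0.050 = 0.791
- S = exp(−3k)/(1 − exp(−12k)) − exp(−3ka)/(1 − exp(−12ka)) = 0.841/0.5 − 0.050 = 1.632
- D/S = 0.485, so the ratio is 0.667 + 0.222 × 0.485 = 0.774

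Over half-lives of 10, 12 and 14 h and ka of 0.6, 1.0 and 1.5, the ratio runs from 0.755 to 0.791.

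**Step 4: DS1 against its own maintenance dose.** Pre-dose, 150/250 = 0.60. At 3 h, multiply the step 3 ratio by 225/250 = 0.9: 0.68 to 0.71. The C1D8 samples therefore see 60% to 71% of DS1's maintenance exposure.

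**Step 5: C2D1.** DS1 has had Days 15-28 at 250 mg BID, 336 h or at least 336/14 = 24 half-lives. The ratio is 250/225 = 1.11, both pre-dose and at 3 h.

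**Step 6: Day 15 itself.** The pre-dose sample is still a 200 mg trough (200/225 = 0.89), and the model gives 0.98-1.01 at 3 h. A sample on that exact day would not yet show the maintenance order.

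**The case against.** The strongest objection is that the governing schedule is not visible. The Cohort A calendar points to Table 8, whose content is not in the public text; Section 6.3.2 is largely blanked; and Section 6.3 refers to the Lab Manual for complete details. Someone reading Section 6.3.3 alone might infer that C1D8 is the only on-treatment PD time in Cohort A2. The documents do not support that: a later DS1/DS2 sample cannot be excluded. This stands, and the fix allows for it.

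Table 7 also lists Cohort A2, A2 DS1 and A2 DS2 as separate rows, so A2 in Section 6.3.3 might mean only the earlier expansion patients. Against this, Section 3.1.1 enrols the DS1/DS2 patients in Cohort A2, and Section 6.3.3 gives them no other rule. If the narrower meaning is intended, the section should say so.

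Two further inferences go too far. One is that 250 mg BID is never measured: Cohort A1 has a flat 250 mg BID level (Table 2) under the same C1D8 rule, so the gap concerns DS1 patients only. The other is that the final RP2D rests on a PD contrast. No section says so. PD was one of four data types in the SRC review and is a named input to cohort expansion (Section 3.3.1), while Section 8.3 says escalation is guided by toxicity because biomarkers are not established, and Section 8.2 says the study is not powered for differences between cohorts. PD is a likely input, not the stated deciding one.

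Finally, the ratios are of exposure, not inhibition. The documents give no exposure-inhibition curve. If inhibition is near its plateau at these doses, the visible PD difference could be small, so one cannot say that DS1 is bound to look weaker. None of this makes C1D8 a valid day on which to compare the schedules.

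**Conclusion.** The concern holds on the visible text. The PKC-β times shown for Cohort A2 put DS1 at 0.67 of DS2 exposure pre-dose and about 0.76-0.79 at 3 h, against 1.11 at maintenance, so C1D8 PD cannot inform the 250 versus 225 mg BID comparison in these 40 patients. The visible PD text was not aligned with the C2D1 PK profile.

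The pre-dose and maintenance ratios need only dose-proportional exposure; the 3 h range also needs the 10-14 h half-life and the assumed absorption rates. Reading the blanked sample name as PKC-β, and Cohort A2 in Section 6.3.3 as including DS1 and DS2, are inferences. The size of any effect on measured inhibition is unknown.

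**What to change.** For DS1 and DS2, collect the PKC-β pre-dose and 3 h pair at C2D1 with the existing PK draws, and keep C1D1 pre-dose as baseline. Alternatively, confirm that Table 8 already has a pair once DS1 is on 250 mg BID (Day 15 onward, and by step 6 preferably some days later) and align Section 6.3.3 with it. In either case, state that any C1D8 PD is reported by dose actually taken and is not used to compare the schedules.

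The cost is small. C2D1 already has a clinic-administered morning dose (Section 5.2.3.1), a 3 h ECG (Appendix 1A) and pre-dose and 3 h PK draws for both schedules (Table 7). On the visible schedule, moving the pair adds no visit and no sampling time; Table 8 would have to confirm this. The downside is losing the one-week PD reading, or one extra pair of samples per patient if it is kept.

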Patients in Cohort B1, B2, and B3. Patients will be treated in 28-day cycles until the combination is no longer tolerated or progressive disease. All patients will continue to be monitored for approximately 30 days (+7 days) after treatment discontinuation for development of any late treatment emergent adverse events. Any adverse events noted only in patients enrolled in Cohort B1 within the DLT evaluation period will be considered in the determination of the maximum tolerated dose/initial RP2D and dose schedule to be taken forward into the expansion phase of the study.

Patients who discontinue combination treatment for progressive disease and/or use of other CLL/SLL therapy will be followed for survival every 24 weeks (± 7 days) for up to 3 years. Patients who discontinue treatment for reasons other than progressive disease, use of other CLL/SLL therapy, death, or withdrawal of consent will have response assessments every 12 weeks (± 7 days) until progressive disease occurs. Thereafter they will be followed for survival every 24 weeks (± 7 days) for up to 3 years. All patients will discontinue survival follow-up upon completion of 3 years of survival follow-up, withdrawal of consent, death, or study closure, whichever is the earliest.

Cohort C

Cohort C1. Once the MTD or initial RP2D is established in A1, Cohort C1 will be initiated. A conventional "3+3" patient enrollment scheme will be followed during this dose escalation Cohort C1. The dose escalation will enroll from 3 to approximately 12 patients. The initial MS-553 dose will be 150 mg BID. Treatment experienced CLL/SLL patients eligible for standard of care venetoclax and rituximab, who are naïve to prior Bcl-2 inhibitor treatment and who have had no more than 2 prior lines of treatment regimens are eligible for this cohort. Starting from Cycle 1, patients will be dosed with MS-553 by mouth twice daily and rituximab according to standard of care, and as outlined in Section 5.2.3.3. Beginning with Cycle 3, venetoclax dosing once daily by mouth will be initiated with weekly dose escalations from 20 mg to 400 mg over 5 weeks per its prescribing information.

Dose level	Cycle 1	Cycle 2	Cycle 3	Cycle 4+	DLT Period(s)
150 mg	150 mg	150 mg	150 mg	150 mg	Cycle 1
BID	BID	BID	BID	BID	through 4
200 mg	200 mg	200 mg	200 mg	200 mg	Cycle 1
BID	BID	BID	BID	BID	through 4

At least two dose levels are planned for Cohort C1. The dosing schedule and DLT evaluation periods are described in the table below.

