In Cohort C1, at least 3 patients will be enrolled at starting dose level of 150 mg BID. The dosing rules for Cohorts A1 and B1 will be similarly applied to Cohort C1. For the dose levels of MS-553 up to and including 225 mg BID, the DLT evaluation period will be through Cycle 4 (16 weeks). During the DLT evaluation period, if \leq 1 DLT is observed, then escalation to the next higher dose level will follow the 3+3 design and proceed when 3/3 or 5/6 patients have completed four treatment cycles without a DLT. If at least 1 of 3 patients experiences a DLT at any dose level, the cohort will be expanded to 6 patients. If \geq 2/3 or \geq 2/6 patients experience a DLT within a cohort, the MTD will be considered to have been exceeded. At Sponsor discretion, additional patients may be enrolled into a cohort where \leq 1 patient develops a DLT to obtain additional safety, PK, PD, and/or efficacy data.

Determination of DLT for dosing Cohorts A1

Each dose cohort will include a minimum of 3 evaluable patients for assessment of DLT. In order to be considered evaluable for DLT, patients must meet at least one of the following criteria:

- 1. Complete one 28-day cycle and receive at least 75% of MS-553 intended doses in Cycle 1
- 2. Discontinue due to DLT

During the DLT evaluation period for each cohort, non-evaluable patients who discontinue treatment before one cycle is complete for reasons other than study drug-related toxicities (e.g., progressive disease, non-compliance), or do not receive at least 75% of MS-553 doses, will be replaced with additional patients enrolled at the same dose level. After a DLT is resolved or reversed to \leq Grade 1, the study drug may continue at a lower dose level at the discretion of the investigator.

A decision on dose escalation to the next dose level will be based on evaluation of the clinical safety profile and may also include evaluation of MS-553 exposure in treated patients. After the completion of each cohort, safety and PK data (if available) will be

reviewed and a decision on dose escalation will be determined by the Investigators, the Safety Review Committee, and the Sponsor.

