3.2. Treatment Duration

Patients will be treated in 28-day cycles. Patients on this study may continue receiving study drug provided they continue to tolerate the drug, have no evidence of progression, do not meet any of the criteria for discontinuation, and the patient's participation in the study has not ended. The anticipated median treatment duration is unknown. Patients who have discontinued treatment for progressive disease and/or who have started another anticancer therapy or an investigational

product, will be followed for survival every 24 weeks (± 7 days) for up to 3 years (follow up can include clinic visit, chart review or telephone contact). Patients who discontinue treatment for reasons other than progressive disease, use of other anticancer therapy or an investigational product, death, or withdrawal of consent will have response assessments every 12 weeks (± 7 days) until progressive disease occurs. Thereafter they will be followed for survival every 24 weeks (± 7 days) for up to 3 years. All patients will discontinue survival follow-up upon completion of 3 years of survival follow-up, withdrawal of consent, death, or study closure, whichever is the earliest. The Sponsor reserves the right to discontinue the study for clinical or administrative reasons at any time.

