3.3.4. Dose Escalation: Combination Cohort C1

Once the MTD or initial RP2D is established for the monotherapy (Cohort A1), enrollment in Cohort C1 will begin. Starting with cycle 1, patients will be dosed with MS-553 by mouth twice daily beginning at 150 mg BID, and rituximab will be started according to standard of care, and as outlined in Section 5.2.3.3. Beginning with Cycle 3, venetoclax dosing once daily by mouth will be initiated with weekly dose escalations from 20 mg to 400 mg over 5 weeks.

At least two dose levels are planned for Cohort C1. The dosing schedule and DLT evaluation periods are described in the table below.

Dose	Cycle 1	Cycle 2	Cycle 3	Cycle 4+	DLT
level					Period(s)
150 mg	150 mg	150 mg	150 mg	150 mg	Cycle 1
BID	BID	BID	BID	BID	through 4
200 mg	200 mg	200 mg	200 mg	200 mg	Cycle 1
BID	BID	BID	BID	BID	through 4

 Table 5:
 Dosing Schedule and DLT Evaluation Periods for Cohort C1

MTD determination, DLT and safety assessments will follow the general principles outlined in Cohort A1. Initial RP2D of MS-553 in the combination therapy is expected to be reached before or when the dose escalation reaches 250 mg BID, the high dose level of MS-553 under testing as monotherapy. Intermediate dose levels (i.e., at 25 mg increment) or lower dose levels may also be evaluated as determined by the Investigators, the Safety Review Committee and Sponsor until the MTD or initial RP2D for the combination is determined.

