5.2.3.3. Venetoclax and Rituximab Dosing – C Cohorts

For patients are enrolled into any of the C series cohorts, venetoclax will be initiated after eight weeks of treatment with MS-553 and rituximab. Rituximab will be administered according to the Full Prescribing Information except the necessary changes to allow for the dosing sequence of the triple drug combination regimen. In order to reduce the risk of TLS, venetoclax will not be administered until Cycle 3. Beginning in Cycle 3, venetoclax will be started and dose escalated in accordance with the Prescribing Information from 20 mg to 400 mg over five (5) weeks and administered in combination with rituximab and MS-533. Venetoclax should be taken with food \geq 6 hr after the morning dose of MS-553. Venetoclax shall be administered in accordance with the Full Prescribing Information.

For patients who have achieved complete responses with the treatment of the triplet regimen of MS-553, venetoclax, and rituximab, assessments of uMRD in a central lab will be performed in a fashion consistent with IWCLL 2018 guideline. If uMRD in both peripheral blood and bone marrow is confirmed in a central lab, MS-553 may be discontinued at the discretion of the investigators after completion of venetoclax administration as defined in package label.

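### On the times stated in section 6.3.3, Cohort C1 has no PKC-β sample before MS-553, so its trough-to-3 h change understates inhibition and cannot be compared with A1, A2 or B1

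*Combined protocol and SAP*

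**What the plan says.** Section 6.3.3 gives two sampling schedules. Samples for Cohorts A1, A2 and B1 will "be collected immediately prior to dosing on Cycle 1 Day 1 and Cycle 1 Day 8 pre-dose and at 3 hr post-dose". The subject of that sentence is cut from the public text; that it means the PKC-β samples is inferred from the parallel sentence on C1. For Cohort C1, PKC-β "biomarker samples will be collected prior to dosing on Cycle 4 Day 1 and pre-dose and at 3 hr post-dose" on Cycle 4 Day 8. The C1 sentence is complete and names Cycle 4 only.

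On treatment, section 3.3.4 says: "Starting with cycle 1, patients will be dosed with MS-553 by mouth twice daily beginning at 150 mg BID". Rituximab also starts in Cycle 1. Under section 5.2.3.3, "venetoclax will be initiated after eight weeks of treatment with MS-553 and rituximab". Section 3.2 says: "Patients will be treated in 28-day cycles".

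Section 6.3.2 describes the samples as a measure of PKC-β signalling in blood cells. Section 8.5.4 admits a patient to the pharmacodynamic population with a single post-treatment sample and does not ask for a baseline.

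**The concern.** Inhibition is a reduction relative to something. In A1, A2 and B1 the reference is the patient's own signal before any MS-553. In C1 every stated sample is taken on the drug, so the pre-dose sample in Cycle 4 is a trough, not a baseline. The Cycle 4 Day 8 pair then measures the swing within a dosing interval. Inhibition that persists through the interval lowers both values and drops out of the comparison.

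At stake is whether target engagement in the triplet can be estimated, and whether it can be set beside monotherapy and the acalabrutinib combination. The synopsis puts C1 at 3 to about 12 patients. A reference missed before the first dose cannot be recovered later, and the rule in section 8.5.4 would not expose the gap.

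**Working it through.** **1. Calendar.** Inputs: 28-day cycles (3.2), MS-553 twice daily from Cycle 1 (3.3.4), venetoclax from Cycle 3 (5.2.3.3). The plan's own figures reproduce: 2 × 28 = 56 days = 8 weeks before venetoclax (5.2.3.3), and 4 × 28 = 112 days = 16 weeks for the C1 DLT window (synopsis).

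- Cycle 4 Day 1 follows 3 × 28 = 84 days of MS-553 (84 × 2 = 168 scheduled doses) and 84 − 56 = 28 days of venetoclax.
- Cycle 4 Day 8 follows 84 + 7 = 91 days of MS-553 and 91 − 56 = 35 days of venetoclax, which is the whole five-week ramp-up (5 × 7 = 35).

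These are nominal; the ±3-day window and lengthened cycles apply.

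**2. Is a pre-dose sample drug-free?** Inputs: half-life 10 to 14 h (1.2.4, single dose in healthy volunteers) and a 12 h dosing interval (5.2.3.1). The fraction left after 12 h is 2^(−12/half-life): 2^(−12/10) = 0.44 and 2^(−12/14) = 0.55. So it is not. The pre-dose samples of Cycle 4 Day 1 and Day 8 are both steady-state troughs. As far as MS-553 is concerned, their expected difference is about zero whatever the inhibition.

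**3. What the Cycle 4 Day 8 pair can show.** Assumptions: mono-exponential decline from 3 h to 12 h, and signal as a fraction of untreated signal equal to 1/(1 + C/IC50).

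- Trough-to-3 h concentration ratio r = 2^(−9/half-life): 0.54 at 10 h and 0.64 at 14 h.
- Let x be the 3 h concentration divided by IC50. True inhibition at 3 h is I = x/(1 + x).
- Signal at trough is 1/(1 + r·x) and at 3 h is 1/(1 + x). The relative fall is 1 − (1 + r·x)/(1 + x) = (1 − r)·x/(1 + x) = (1 − r)·I.

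| x | True inhibition at 3 h | Relative fall, r = 0.54 | Relative fall, r = 0.64 |
|---|---|---|---|
| 1 | 50% | 23% | 18% |
| 4 | 80% | 37% | 29% |
| 19 | 95% | 44% | 34% |
| limit | 100% | 46% | 36% |

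The fall understates inhibition throughout and is capped at 1 − r.

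**4. With a reference before the first dose.** The denominator becomes the untreated signal, so the fall at 3 h equals I: 50%, 80% and 95% in the three rows. This is the quantity that the A1, A2 and B1 schedule yields.

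**The case against.** **The schedule is not fully visible.** Table 8, to which the Cohort C calendar defers, and the Cohort C specimen list in the synopsis are not shown. Section 6.3.3 also keeps a fragment about collection on Cycle 1 Day 1 whose subject is cut, and section 6.3 leaves full details to the Lab Manual. A Cycle 1 Day 1 PKC-β sample for C1 therefore cannot be excluded. This stands, and it limits the point to the times stated in section 6.3.3. Footnote j of Appendix 1C mentions a 3 h draw on Cycle 1 Days 1 and 8, but it matches the A and B calendars, and a 3 h draw would not be a baseline.

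**Cycle 4 may be deliberate.** It lets the full triplet be observed. That is a sound reason for the Cycle 4 Day 8 pair, but not for having no earlier reference.

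**The swing could be corrected.** Under the model above, dividing the fall by 1 − r returns I. The answer would then rest on the model. With an assumed 10% of signal that cannot be inhibited (r = 0.54), the relative fall is 27.5% at x = 4 and 19.7% at x = 19, and that correction fails.

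**Two stronger readings should not be drawn.** A reader might infer that a more active dose would look weaker. At a fixed ratio the relative fall rises with inhibition and only levels off. Section 1.2.4 reports a half-life that did not appear to depend on dose and mostly dose-proportional exposure, which argues for a roughly constant ratio. Reversal needs something more: an absolute rather than a relative fall (15.1, 11.8 and 3.9 points of untreated signal at x = 1, 4 and 19, r = 0.54), a ratio that differs between doses, or a residual signal. The documents establish none of these.

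A reader might also infer that C1 dose decisions would be misled. The explicit uses of pharmacodynamic data concern A1 and A2 and the 100 mg fallback (3.3.1, 3.3.2). For C1 the synopsis has the Safety Review Committee look at safety, tolerability and PK; section 3.5 lists demographics, PK and safety; section 8.3 says that escalation follows toxicity.

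**Conclusion.** The point holds, subject to Table 8. Every Cohort C1 PKC-β sample stated in section 6.3.3 follows at least 84 nominal days of MS-553, so there is no unexposed reference. What remains is a trough-to-3 h change that, under the stated model and a ratio of 0.54 to 0.64, shows only 36% to 46% of the true inhibition and cannot be placed on the A1, A2 and B1 scale. The ratio comes from healthy-volunteer, single-dose half-lives and may differ in patients on the triplet. The absence of a reference does not depend on it.

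The consequence is modest. PKC-β inhibition is not a primary or secondary endpoint, and section 8.4 states no formal hypothesis. Only exploratory conclusions on target engagement in the triplet are affected. It is still worth correcting before further C1 patients start treatment.

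**What to change.** Check Table 8 and the Lab Manual first. If they already hold a C1 PKC-β sample before the first MS-553 dose, align section 6.3.3 with them. If not, change all three: take the C1 reference sample before the first MS-553 dose on Cycle 1 Day 1 in place of the Cycle 4 Day 1 pre-dose sample, and keep the pre-dose and 3 h pair on Cycle 4 Day 8. Do not move the pair to Cycle 1 Day 8: venetoclax has not started then, and the triplet measurement would be lost.

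Cost: one line in each place. The count stays at three samples per patient, and blood is already drawn on Cycle 1 Day 1 for blood count and chemistry (Appendix 1C).

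Downsides: the Cycle 4 Day 1 trough is lost, although the Cycle 4 Day 8 pre-dose sample is a similar steady-state trough. As Table 7 reads, Cycle 4 Day 1 is also a day with a full MS-553 PK profile; keeping that sample as well would cost one more per patient. The comparison of Cycle 4 Day 8 with Cycle 1 Day 1 needs a stated caveat that rituximab and venetoclax may have changed the sampled cells by then.
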